#### 15.6 Analysis of Secondary Objectives

- o For safety analysis, adverse events will be summarized by type and grade.
- To determine whether SBRT combined with concurrent CBI results in statistically significant improvements in anti-tumor immune responses compared to CBI alone we will perform immunologic assays quantifying lymphocyte specificity and activation, including Immune cell Sequencing, ProtoArrays, Immunoassays, and multiparametric flow cytometry.
- O Hazard rate estimates and 95% confidence intervals as well as Kaplan-Meier (KM) estimates will be used to summarize survival (OS), progression free survival (PFS), time to locoregional progression (TTLP) and time to distant progression (TTDP), duration of response functions over time, and stable disease (SD). The median OS, PFS, TTLP, TTDP, and SD will be reported.

#### 15.7 Evaluation of Toxicity

All patients will be evaluable for toxicity from the time of their first treatment of CBI.

#### 15.8 Evaluation of Response

All patients included in the study must be assessed for response to treatment, even if there are major protocol treatment deviations or if they are ineligible. Each patient will be assigned one of the following categories: 1) complete response, 2) partial response, 3) stable disease, 4) progressive disease, 5) early death from malignant disease, 6) early death from toxicity, 7) early death because of other cause, or 8) unknown (not assessable, insufficient data).

All of the patients who met the eligibility criteria (with the possible exception of those who received no study medication) should be included in the main analysis of the response rate. Patients in response categories 4-8 should be considered to have a treatment failure (disease progression).

All conclusions should be based on all eligible patients. Sub-analyses may then be performed on the basis of a subset of patients, excluding those for whom major protocol deviations have been identified (e.g., early death due to other reasons, early discontinuation of treatment, major protocol violations, etc.). However, these sub-analyses may not serve as the basis for drawing conclusions concerning treatment efficacy, and the reasons for excluding patients from the analysis should be clearly reported. The reason for performing subset analyses would be to generate hypotheses for future prospective clinical trials.

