#### 5. PARTICIPANT SELECTION AND ENROLLEMENT CRITERION

#### 5.1 Inclusion Criteria

- 5.1.1 The PI or Co-Investigator Radiation Oncologist states that one of the lesions can be treated with SBRT.
- 5.1.2 Patient must have at least 1 site of measurable disease by Response Evaluation Criteria in Solid Tumors (RECIST) 1.1 criteria on computed tomography (CT) or Magnetic resonance imaging (MRI) which will not be irradiated.
- 5.1.3 Histological confirmation of malignancy (primary or metastatic tumor).
- 5.1.4 Patient may have any prior therapy allowed aside from having had prior radiotherapy to the treatment site (see exclusion criteria 5.2.3).
- 5.1.5 Patient must be  $\geq 3$  years of age.
- 5.1.6 Lansky scale score of  $\geq$ 70 (ages  $\geq$  3 or < 16 years) OR Karnofsky scale score of  $\geq$ 70 (ages  $\geq$  16 or < 18 years) OR ECOG performance status  $\leq$  2 (18 years or older).
- 5.1.7 Patient's screening laboratory values must meet the following criteria:

Leukocytes $\geq 2,000/\mu L$ Absolute Neutrophil Count $\geq 1,000/\mu L$ Platelets $\geq 50,000/\mu L$ 

Total bilirubin \leq 2x institutional upper limit of normal
AST(SGOT)/ALT(SGPT) <2.5 X institutional upper limit of

normal

Serum creatinine  $\leq 1.5x$  ULN or creatinine clearance  $(CrCl) \geq 40$  mL/min (using the

Cockcroft-Gault formula):

- (1) Female CrCl = (140 age in years) x weight in kg x 0.85 /72 x serum creatinine in mg/dL
- (2) Male CrCl = (140 age in years) x weight in kg x 1.00/72 x serum creatinine in mg/dL

Pulse Oximetry

≥92% on Room Air at Rest

- 5.1.8 Patient or parent/legal guardian must have the ability to understand and the willingness to sign a written informed consent document.
- 5.1.9 For Patients <18 years of age, enrollment on trial and potential for use of CBI or CBI combined with SBRT must be agreed upon by consensus opinion of a multidisciplinary pediatric tumor board.

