#### 5.2 Exclusion Criteria

5.2.1 Patient has had chemotherapy or radiotherapy within 4 weeks prior to entering the study or those who have not recovered from adverse events due to agents

administered more than 4 weeks earlier.

- 5.2.2 Patient receiving any investigational or experimental agents other than immunotherapy.
- 5.2.3 Patient who has had any prior radiotherapy to the treatment site(s).
- 5.2.4 Patient is a pregnant woman (pregnant women are excluded from this study because radiation treatment has known potential for teratogenic or abortifacient effects).
- 5.2.5 Patient refuses to sign informed consent.

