#### **6.2** Therapeutic Procedures

Patients will be pre-screened for eligibility and should be enrolled and randomized prior to starting immunotherapy. However, patients who have started immunotherapy up to 5 days prior to enrollment will be still be eligible for screening, randomization, and enrollment.

Upon confirmation of eligibility and enrollment in the study, the following will be completed:

- 1) Demographics review, medical history and clinical exam
- 2) Review of concurrent medications
- 3) Vital signs, height and weight
- 4) Laboratory Bloodwork including: CBC, BMP, LFT.
- 5) Plasma and Peripheral blood mononuclear cells will be collected and subsequently frozen for immune monitoring assays.
- 6) Tumor measurements (Recist 1.1) within 4 weeks prior to start of CBI

Upon randomization into the SBRT arm of the protocol, patients will be seen by at least one of the Co-Investigator Radiation Oncologists. CT simulation will be performed with fabrication of a radiation therapy immobilization device (such as a Vac-Lok) which will be custom made for each patient. The treating radiation

oncologist will identify the location of the tumor. Gross tumor volume (GTV) delineation will be performed on sequential axial computed tomography images. An SBRT treatment plan will be developed based on tumor size and location. The dose will be prescribed to the minimal isodose line that completely covers the GTV plus a 5 mm margin. Adjacent normal structures including but not limited to the chest wall, spinal cord, heart, esophagus, aorta, kidneys, rectum, bowel, liver, and stomach within 5 cm of the GTV will be identified for the purpose of limiting incidental radiation to these structures.

In addition, prior to treatment delivery, a four-dimensional cone beam CT study will be performed on individual patients to assess respiration in these patients and to determine tumor targeting accuracy for those tumors that may be subject to respiratory motion such as those in the lung, abdomen, or liver. If tumor motion is greater than 5 mm, the planning target volume (PTV) will be expanded to account for respiration.

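### The eligible-only response analysis in section 15.8 permits exclusions after randomisation, and these may fall more readily on the SBRT arm

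*Combined protocol and SAP*

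**What the plan says.** Section 15.8 first asks that every patient in the study be assessed for response, "even if there are major protocol treatment deviations or if they are ineligible". It therefore expects some patients to be found ineligible after entry. It then narrows the main analysis: "All of the patients who met the eligibility criteria (with the possible exception of those who received no study medication) should be included". It adds: "All conclusions should be based on all eligible patients". Response categories 4 to 8, which include early deaths (5 to 7) and unassessable patients (8), count as failures.

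The relevant eligibility criteria are these:
- 5.1.1, for every patient: "The PI or Co-Investigator Radiation Oncologist states that one of the lesions can be treated with SBRT".
- 5.1.2: at least one site measurable "on computed tomography (CT) or Magnetic resonance imaging (MRI) which will not be irradiated".
- 5.2.3, echoed in 5.1.4: no earlier radiotherapy to the site that is to be treated.

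On timing, 6.2 confirms eligibility at entry ("Upon confirmation of eligibility and enrollment in the study, the following will be completed"). The radiation work-up comes later and in one arm: "Upon randomization into the SBRT arm of the protocol, patients will be seen by at least one of the Co-Investigator Radiation Oncologists". Simulation, contouring and planning follow that visit.

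Two other sections define different populations. Section 15.5 describes the primary analysis population as those who received all three SBRT fractions. Section 11.2 requires at least one CBI cycle and, for objective response, a repeat disease evaluation.

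**The concern.** Removing patients after randomisation is harmless only if removal is unrelated to arm or unrelated to outcome. Here the first condition is doubtful. Criteria 5.1.2 and 5.2.3 turn on which lesion is irradiated. In the SBRT arm that choice is fixed and examined closely after randomisation; in the control arm it never is. A missed failure of either criterion is therefore more likely to surface in the SBRT arm, and whoever rules on it knows the arm, since no masking is described.

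For 5.1.2 the direction of bias is plausible. The synopsis reads response from non-irradiated lesions. An SBRT patient left without a measurable non-irradiated lesion has nothing to read, so falls in category 8 and counts as a failure. If the patient is ruled ineligible instead, that failure leaves the denominator. A control with the same disease stays assessable. For 5.2.3 the documents do not show the direction.

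The wording on patients who received no study medication leaves a second exclusion undecided, to be settled when the arm is known.

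**Working it through.** **1. The plan's own figure.** The synopsis and 15.2 give 146 patients, 73 per arm, one-tailed, 80% power. Section 15.2 prints the significance level as 0.05%; 5% is the value that fits. For 61% against 81%, with pooled rate 0.71:

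n = [1.645·√(2·0.71·0.29) + 0.842·√(0.61·0.39 + 0.81·0.19)]² / 0.20² = (1.056 + 0.527)² / 0.04 ≈ 62.6, so 63 per arm.

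With continuity correction: (62.6/4)·[1 + √(1 + 4/(62.6·0.20))]² ≈ 72.3, so 73 per arm, or 146. The figure is reproduced for the dual-agent melanoma case. The tumour-type weights mentioned in 15.2 are not given, so the weighted calculation cannot be repeated.

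**2. Model for one-sided exclusion.** The documents give no expected number of ineligible patients, so this is an assumption. Both arms have true response rate p and 73 patients. Each SBRT non-responder is removed with probability q, and no control is removed. If K are removed, the test is

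z = [X_S/(73−K) − X_C/73] / √{p̂(1−p̂)[1/(73−K) + 1/73]}, with p̂ = (X_S + X_C)/(146−K), rejecting when z > 1.645.

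The expected number removed is 73(1−p)q. The apparent SBRT rate is about p/[1 − q(1−p)]. Error rates are by exact binomial enumeration.

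| p (both arms) | Removed at q = 10% | Apparent SBRT rate | Error, q = 0 | Error, q = 10% |
|---|---|---|---|---|
| 30% | 73·0.70·0.10 = 5.1 | 0.30/0.930 = 32.3% | 5.0% | 8.9% |
| 45% | 73·0.55·0.10 = 4.0 | 0.45/0.945 = 47.6% | 5.7% | 9.5% |
| 55% | 73·0.45·0.10 = 3.3 | 0.55/0.955 = 57.6% | 5.7% | 9.2% |

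At p = 45%, q = 5% gives 7.2% and q = 15% gives 12.4%.

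**3. Fixed numbers removed, at the control rates in 15.2.** Exactly k SBRT non-responders are removed:

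| k | p = 25% | p = 40% | p = 61% |
|---|---|---|---|
| 0 | 5.0% | 5.4% | 5.3% |
| 2 | 6.1% | 7.5% | 7.9% |
| 4 | 7.7% | 10.2% | 12.1% |

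The row k = 0 is also the result when all randomised patients are analysed by arm.

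**4. Weaker links to outcome.** Take p = 45% and remove four SBRT patients.
- If they never respond, the retained rate is 73·0.45/69 = 47.6% and the error is 10.3%.
- If they respond at half the average rate, the retained rate is (32.85 − 4·0.225)/69 = 46.3% and the error is 7.8%.
- If they respond at the average rate, the retained rate stays 45% and the error is 5.8%, against 5.7% with nobody removed.

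**The case against.** The strongest reply is that both criteria can be applied to both arms. Criterion 5.1.1 requires a treatable lesion for every patient, and 6.2 confirms eligibility at enrolment. A control whose only candidate lesion had already been irradiated, or whose only measurable lesion is the candidate, could be ruled ineligible too. Nothing in 6.2 says that eligibility is judged again during planning.

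This stands against the stronger reading that a reader might infer: that only SBRT patients can fail these criteria, so that 15.8 strikes patients from that arm alone. The documents do not support that. Other criteria can also remove patients from either arm, and the clause on untreated patients is neutral in wording because both arms receive CBI.

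Two tempting examples also fail. Heavy pretreatment is not a failed criterion, since 5.1.4 allows any prior therapy except radiotherapy to the treatment site. A site that proves untreatable at planning is a treatment deviation, and 15.8 allows deviations to be excluded only in sub-analyses that cannot support conclusions.

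The size is open to challenge as well. SBRT falls within days 1 to 21 of the first cycle and response is read at week 16, so, apart from patients left with no lesion to read, an exclusion made at planning can track outcome only through prognosis.

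What remains is unequal detection. Criterion 5.1.1 asks only that one of the lesions be treatable. No text requires that lesion to be recorded before randomisation, or eligibility to be judged on pre-randomisation data by someone unaware of the arm.

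**Conclusion.** The concern holds as a risk that the plan leaves open. Section 15.8 clearly makes eligibility, which may be ruled on after randomisation, the filter for the main response analysis and for every conclusion. That the filter bears more on the SBRT arm is an inference from 5.1.2, 5.2.3 and 6.2, and no section prescribes it.

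The size cannot be derived from the documents. The one-sided error of about 9-10% rests on three assumptions: 10% of SBRT non-responders are removed, no SBRT responder is removed, and no control is removed. That is a worst case for the assumed exclusion rate. The apparent gain in it is 2 to 3 percentage points. A partial link to prognosis gives less, and no link gives none.

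The point survives the conflict between sections: choosing 15.8 over 15.5 or 11.2 would leave it in place. The restriction in 15.5 to patients with three SBRT fractions depends on arm more directly and must be reconciled at the same time. The change is worth making because it is cheap and closes the route to bias whatever its true size.

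**What to change.** In 15.8, replace the two eligibility sentences with a rule to this effect: the main response analysis includes every randomised patient in the arm assigned, whether or not later found ineligible and whether or not treatment was started; a patient without an assessable 16-week read is a non-responder in the applicable category (5 to 7 for early deaths, otherwise 8). Move the eligible-only analysis to the sub-analyses that 15.8 already bars from supporting conclusions.

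Make the population in 15.5 and the evaluable definitions in 11.2 agree with this. A useful addition is to record, for every patient before randomisation, the intended SBRT lesion and the measurable lesion(s) to be left unirradiated, and to judge eligibility for the supportive analysis on pre-randomisation data, blind to arm.

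The cost is wording in three sections and, with the addition, one baseline record. There is slight dilution. For example, if four of 73 SBRT patients gain nothing and respond at 61%, the arm's rate is (69·0.81 + 4·0.61)/73 = 79.9% instead of 81%. An SBRT patient with no non-irradiated lesion to read would count as a failure while a similar control stays assessable, which works against SBRT; recording both lesions beforehand should keep such cases few.
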